1. PREVIOUS STUDY HISTORY

Has this study ever been reviewed and rejected/disapproved by another IRB prior to submission to this IRB?
No ☐ Yes – if yes, please explain:

2. BRIEF SUMMARY OF RESEARCH

- The summary should be written in language intelligible to a moderately educated, non-scientific layperson.
- It should contain a clear statement of the rationale and hypothesis of your study, a concise description of the methodology, with an emphasis on what will happen to the subjects, and a discussion of the results.
- This section should be ½ page

Approximately 100,000 adolescents and young adults in the United States experience a first episode of psychosis (FEP) each year. Psychotic symptoms typically emerge during formative years of development and interfere with the establishment of healthy educational, vocational, and social foundations. Despite the severity of symptoms and significant decline in functioning, the time between symptom onset and receiving appropriate care in the U.S. is lengthy¹. Results from the NIMH-funded Recovery After an Initial Schizophrenia Episode - Early Treatment Program (RAISE-ETP) conducted at 34 community clinics across 21 states throughout the U.S., involving 404 FEP patients, indicated a median duration of untreated psychosis (DUP) of 74 weeks². Longer DUP has been shown to independently predict negative outcomes, including poorer response to treatment, worse global, vocational, social, and cognitive functioning, higher risk of relapse, greater symptom severity, and poorer quality of life^{1,3,4}. As psychotic symptoms persist and disability accumulates, individuals with FEP are missing a critical period to benefit from effective early intervention services. Over the past decade, there have been increasing efforts to understand and mitigate contributing factors to increased DUP in order to inform the development of effective early intervention services, increase chances of recovery, and improve long term outcomes in individuals with psychotic disorders.

Prior successful DUP reduction initiatives^{5,6} have utilized various marketing strategies including print (brochures, newspapers, pamphlets, postcards), broadcast (radio, television, cinema), and telephone contact, to educate the general public about early intervention services. These strategies, however, are expensive, inefficient, and outdated. Online outreach, supported by technological innovation, offers the prospect of reaching individuals earlier in

Version Date: 6.9.22 Page 3 of 31

the course of illness development, as well as individuals who might not otherwise come into contact with traditional referral sources. In response to this challenge, Northwell Health's early psychosis research team is collaborating with Strong365, a nonprofit initiative dedicated to raising early psychosis intervention awareness, to develop and test a proactive and targeted comprehensive digital media marketing campaign designed to facilitate help-seeking and encourage treatment initiation in prospective patients with FEP and their caregivers. Our team will take advantage of search engine advertising, which allows advertisers (researchers) to select keywords/phrases and create linked advertisements appearing as a strategically placed search result. Our dedicated ads will appear in response to online search queries conducted by prospective patients and their caregivers throughout New York State (NYS) that align with the campaign's pre-selected keywords/phrases. Individuals who click on the ads will be immediately directed to our campaign landing page/website, and offered a variety of established, innovative, and interactive online engagement tools intended to instantly connect users with coordinated specialty care (CSC) staff and to facilitate earlier treatment initiation.

Campaign referrals will be centralized and individuals with FEP will be enrolled into OnTrackNY (OTNY), a network of 21 dedicated early psychosis intervention programs throughout NYS. The campaign will target individuals as well as their friends, family, and caregivers, searching for information online. We will measure the DUP of individuals enrolled into OTNY before and after campaign activation and track the impact of the campaign on the number of FEP referrals and number of patients admitted to OTNY in NYS. Furthermore, we aim to identify the campaign target audience most effective at promoting treatment initiation as well as the online tools and resources most effective at encouraging treatment initiation of identified individuals with FEP. We will additionally explore the online trajectories to care of individuals with FEP engaging with the campaign.

Results from this initiative will provide novel online strategies for achieving rapid initiation of appropriate specialty care throughout NYS. These data will also help map the online trajectories to specialty care, identify ongoing barriers and bottlenecks, and support the development of new practical, reproducible, and cost effective strategies to achieve substantial DUP reduction in the U.S.

3. INTRODUCTION/BACKGROUND MATERIAL/PRELIMINARY STUDIES AND SIGNIFICANCE

• Describe and provide the results of previous work by yourself or others, including animal studies, laboratory studies, pilot studies, pre-clinical and/or clinical studies involving the compound or device to be studied.

Version Date: 6.9.22 Page 4 of 31

- Include information as to why you are conducting the study and how the study differs from what has been previously researched, including what the knowledge gaps are.
- Describe the importance of the knowledge expected to result

The consequences of untreated psychoses can be devastating⁷. The public health challenge of appropriate early intervention and treatment is exacerbated by the fact that the incidence of psychosis is relatively low, and that individuals who develop psychotic symptoms may not be ready to accept help, and may even be suspicious of those trying to help them. Further, there is little public awareness as to the nature of psychotic illnesses and such illnesses are still often associated with considerable discrimination. Despite international efforts to improve access to state-of-the-art FEP programs, data from the NIMH funded RAISE-ETP project support the hypothesis that such programs, in and of themselves, are not sufficient to reduce DUP. Novel, innovative, and focused strategies that act beyond traditional outreach and intake processes are necessary in order to accomplish this crucial goal.

Several initiatives in a number of countries have been implemented in order to reduce DUP with varying degrees of success¹⁰. Many have directed efforts towards educating family physicians and other health service providers, whereas some studies have targeted schools and the general public. Community educational programs have thus far demonstrated the most promise in reducing DUP through widespread marketing campaigns and easily accessible services. The TIPS project in Norway⁵ and the EPIP project in Singapore⁶ both successfully utilized mass-media to educate the general public and relevant professionals regarding the benefits of early intervention and available services. In the U.S, a similar early detection program is currently underway9 which integrates community outreach with an online component. These strategies, however, require extensive and costly resources and organization, and focus on broadly and nonspecifically improving general public education and awareness. Limited efforts have attempted to harness available modern technological resources to more precisely and proactively target and engage prospective patients and their caregivers in order to reduce DUP.

Online outreach, supported by technological innovation, may prove critical to expediting help-seeking and facilitating specialty care treatment initiation in prospective patients with FEP and their caregivers. The Internet provides an unparalleled opportunity to diminish barriers to accessing services by reaching people earlier in the course of illness and promoting engagement with services that meet their needs, while reducing health disparities among vulnerable populations¹⁰. Google has been consistently ranked as the world's most popular search engine with over 660 million daily visitors, managing over three billion searches daily¹¹. Reports have found that at least 80% of Internet users search online for health related information¹² including mental

Version Date: 6.9.22 Page 5 of 31

health. Importantly, many individuals utilizing the Internet for mental health resources have yet to connect with psychiatric care¹³.

Searching online has become the primary resource for youth seeking out mental health information ¹⁴. This is especially true for stigmatized illnesses such as schizophrenia as the Internet provides a comfortable and anonymous setting to gather information about symptoms and treatment options ¹⁵. We demonstrated that participants with FEP reported utilizing the Internet first, and most frequently, to gather information prior to receiving psychiatric care while psychotic symptoms were emerging ^{16,17}. Youth with FEP were more likely to search online for information as opposed to, or prior to, discussing with peers, family, physicians, and mental health clinicians. Moreover, the Internet has increasingly become an important source of referrals to FEP programs ¹⁸. The Internet may represent one of the first proactive steps towards treatment initiation ¹⁶ and information gathered online appears capable of impacting mental health related help-seeking behavior ¹⁹.

There is an unexplored opportunity to harness the Internet's far reaching platform to improve early detection and intervention for psychosis. Given that adolescents and young adults in the early stages of psychotic illness, as well as their caregivers, are known to be online, searching for information, prior to receiving formal diagnoses and treatment, and throughout the DUP, we propose to capitalize on the immense power of existing and accessible online engagement tools in order to identify and meaningfully interact with patients with FEP and their caregivers, providing them with instant information and resources, designed to move them along their trajectory to care, and facilitate earlier linkage to specialty services.

4. OBJECTIVE(S)/SPECIFIC AIMS AND HYPOTHESES

- A concise statement of the goal(s) of the current study.
- *The rationale for and specific objectives of the study.*
- The goals and the hypothesis to be tested should be stated.

Aim 1: Evaluate the effectiveness of a search engine ad campaign on reducing DUP and raising rates of FEP referrals by directly comparing DUP and FEP referrals pre-campaign to DUP and FEP referrals during the campaign. Hypothesis A: Patients admitted to OTNY via campaign channels will demonstrate significantly shorter DUP than those admitted to OTNY through traditional outreach prior to campaign activation. Hypothesis B: Activating the campaign will significantly increase the number of FEP referrals and patients admitted to OTNY as compared to the number of FEP referrals and patients to OTNY admitted pre-campaign activation.

Version Date: 6.9.22 Page 6 of 31

Aim 2: Determine the efficacy of a campaign targeting caregivers in promoting treatment initiation by comparing rates of OTNY enrollment arriving through the caregiver campaign to rates of enrollment arriving through the patient campaign. Hypothesis: Engaging caregivers online will significantly increase the likelihood of promoting treatment initiation for individuals with FEP as compared to engaging prospective patients online. Aim 3: Explore which methods of online engagement are most effective at promoting treatment initiation by comparing rates of OTNY enrollment of individuals with FEP interacting with research staff via two-way video and live chat to rates of enrollment of individuals with FEP utilizing text, email, and/or phone alone. Hypothesis: Individuals with FEP who engage via two-way video and live chat will be significantly more likely to initiate in-person contact compared to individuals with FEP who engage via text, email, and/or phone alone.

6. RECRUITMENT METHODS

- *Describe the source of potential subjects*
- Describe the methods that will be used to identify potential subjects
- Describe any materials that will be used to recruit subjects. A copy of any advertisements (flyers, radio scripts, etc.) should be submitted along with the protocol.
- If monetary compensation is to be offered, this should be indicated in the protocol

Referrals for the study will come from self-response to the search engine ads. Those individual who interact with research staff via phone, text, email, live chat, or two way video will be greeted by a member of the study team who will inform users that as part of efforts to improve services, we'll be using some of the information provided to connect them to local care. If the individual does not want their information shared they can opt out. Patients who on initial evaluation are deemed not to be capable of giving verbal informed consent will not be evaluated further for the study. Patients who are deemed capable of giving verbal informed consent will then be provided with a full and complete description of the study.

Participants who are deemed most likely to be eligible for a referral to an early intervention clinic (based on their responses to the self-screener and/or live chat with research staff) and who choose not to progress along their pathway to care and/or accept a referral to care, will be re-approached by research staff (via the provided contact information) to participate in an additional optional 10 minute qualitative interview. Verbal consent for completion of this additional interview will be obtained. The goal of the interview will be to explore barriers in the online pathways to care and ultimately improve future iterations of the campaign. Questions will be open ended and explore personal motivations for deciding against pursuing formal care at this time.

7. ELIGIBILITY CRITERIA

- Describe the characteristics of the subject population, including their anticipated number, age, ranges, sex, ethnic background, and health status. Identify the criteria for inclusion or exclusion of any subpopulation.
- Explain the rationale for the involvement of special classes of subjects, such as fetuses, pregnant women, children, prisoners or other institutionalized individuals, or others who are likely to be vulnerable. You cannot include these populations in your research, unless you indicate such in the protocol
- Similarly, detail exclusionary criteria: age limits, special populations (minors, pregnant women, decisionally impaired), use of concomitant medications, subjects with other diseases, severity of illness, etc.

Version Date: 6.9.22 Page 8 of 31

Given that ads will appear in response to any online search query conducted by any individual in NYS that align with the campaign's keywords, we will likely interact with many individuals searching for behavioral health information online. All campaign related inquiries will be recorded centrally by research staff. Individuals experiencing FEP will be referred to OTNY.

OTNY Inclusion criteria include: 1) DSM-V diagnosis of schizophrenia, schizophreniform, schizoaffective disorder, brief psychotic disorder, delusional disorder, unspecified schizophrenia spectrum disorder, assessed via clinical interview; 2) psychotic symptom onset within the past two years; 3) ages 16 to 30 years; 4) NYS resident

OTNY Exclusion criteria include: 1) diagnosis of substance-induced psychotic disorder, a psychotic disorder due to a general medical condition, or mood disorder with psychotic features; 2) Intellectual disability (IQ < 70) or autistic spectrum disorder assessed by clinical interview.

All individuals who meet OTNY inclusion criteria will be offered care regardless of insurance status or ability to pay. All ineligible OTNY referrals will be referred to appropriate local services.

8. NUMBER OF SUBJECTS

- Indicate the total number of subjects to be accrued locally. If applicable, distinguish between the number of subjects who are expected to be pre-screened, enrolled (consent obtained), randomized and complete the research procedures.
- If your study includes different cohorts, include the total number of subjects in each cohort.
- If this is multisite study, include total number of subjects across all sites.

OTNY receives on average 34 referrals weekly, of which, on average 26% are found eligible, and 8 new FEP patients are enrolled in NYS each week. Based on existing OTNY inquiry data as well as the results of our prior pilot initiatives, we anticipate approximately doubling weekly inquiries as a result of the campaign, arriving through campaign related channels over the course of the trial (30 additional referrals). Of those, we anticipate that 20% will be appropriate for OTNY (6 participants weekly) and that 4 of those individuals will be successfully enrolled each week as a result of the campaign.

Version Date: 6.9.22 Page 9 of 31

9. STUDY TIMELINES

- *Describe the duration of an individuals participation in the study*
- Describe the duration anticipated to enroll all study subjects
- The estimated date of study completion

Phase 1 (6 Months): Development and optimization of campaign ads and landing page, begin collecting baseline OTNY referral and DUP data.
Phase 2 (18 Months): Campaign deployment and data gathering.
Phase 3 (6 Months): Data cleaning, analysis, and manuscript preparation.
Participation will end once an individual accepts or refuses an outpatient referral.

10. ENDPOINTS

- Describe the primary and secondary study endpoints
- Describe any primary or secondary safety endpoints

N/A

11. RESEARCH PROCEDURES

- Include a detailed description of all procedures to be performed on the research subject and the schedule for each procedure.
- *Include any screening procedures for eligibility and/or baseline diagnostic tests*
- Include procedures being performed to monitor subjects for safety or minimize risks
- *Include information about drug washout periods*
- If drugs or biologics are being administered provide information on dosing and route of administration
- Clearly indicate which procedures are only being conducted for research purposes.
- If any specimens will be used for this research, explain whether they are being collected specifically for research purposes.
- Describe any source records that will be used to collect data about subjects
- *Indicate the data to be collected, including long term follow-up*

We will develop and test two comprehensive digital media campaigns running in parallel. The first campaign will target prospective patients searching online for information. The second will target caregivers. Each campaign will run simultaneously and will each be comprised of their own search engine ads/ results and dedicated landing page both geared specifically towards their respective target audience. The ads and their associated landing page/website will be selected and displayed automatically based on the keywords/search terms entered by an individual user online as well as the age of individual searching. The campaign will be accessible both via desktop and mobile.

Version Date: 6.9.22 Page 10 of 31

For each campaign, a landing page will be developed with the primary goal of facilitating treatment initiation for individuals with FEP and their caregivers searching for information online in NYS. In order to optimize website visibility, the landing page will focus on core messages derived from our initial evaluations that were found to be most relevant to information seeking individuals. These include accurately identifying and understanding early signs and symptoms of psychosis and finding local support. The landing page content will be driven by ETP staff along with input from Strong365's development team. Additional input will be obtained from existing ETP participants with lived FEP experience.

The campaign website page will offer:

- 1) **Education.** The website will be designed to be an interactive educational experience encouraging visitors to effortlessly communicate directly with research staff online via live chat, over the phone, text, or email. The landing page will include information regarding signs and symptoms of psychosis as well as available local service options. The information will be displayed in a simple yet informative, youth friendly, and engaging manner utilizing text, images, videos, and animations.
- 2) **Needs assessment**. An online survey will be designed to obtain demographic information regarding the individuals visiting the campaign landing page, the motivations supporting their search, as well as their desired outcome. Responses are encouraged though not required in order to proceed. The survey will consist of 7 multiple choice questions with additional open ended response options.
- 3) **Quick clinical connection.** The landing page will offer easy and efficient access to research staff including a licensed mental health counselor through dedicated campaign email and phone number for calling and texting. Users may leave their own personal contact details if they prefer that someone from the team contact them directly. Staff will be available 12 hours daily during the week and 6 hours daily on weekends. Staffing availability will be flexible and dependent on peak website traffic as well as the needs and requests of users.
- 4) **Live chat.** The landing page will offer an opportunity to chat live with a licensed mental health clinician using an online pop up chat option. Staff will be available 12 hours daily throughout the week and 6 hours daily during the weekend. Hours will fluctuate depending on identified peak online activity when users are most active. Users will also be offered the opportunity to schedule a virtual video chat with a clinician via two-way video, providing an opportunity for face to face interaction.

Version Date: 6.9.22 Page 11 of 31

5) The Prodromal Questionnaire-Brief (PQ-B). The PQ-B is a 21 item evidence-based screening tool used to assess psychosis risk³⁴. During our pilot project, Fifteen percent (n=671) of visitors completed the PQ-B and 453 (67.5%) scored positive suggesting the presence of psychotic experiences. The caregiver campaign will offer the unpublished parent PQ-B designed to obtain caregivers' perspectives of emerging experiences in a loved one. Users who complete the questionnaire will be offered the opportunity to download a copy of their results and all will be encouraged to instantly discuss scores with research staff online.

Clinical research material will be obtained through a variety of mechanisms. Participants may choose to complete our online demographic survey/needs assessment as well as the psychosis screener (PQ-B). Participants who choose to leave contact information will be contacted via their preferred method including email, phone, and text. Participants may also choose to interact with research staff directly via live chat and two way video available on our campaign website. All information gained from theses interactions will be recorded by research staff and kept confidential. Any notes and test results obtained as part of the engagement and referral process will be treated with the same stringent confidentiality as treatment as usual. Investigators will collect the results of the referral and eligibility assessment. Qualitative interviews and assessments done with participants and collateral sources will be collected and kept confidential. Online activity including engagement with campaign advertisements and website will be tracked by Google analytics and sent to research staff on a weekly basis.

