Aim 2: Determine the efficacy of a campaign targeting caregivers in promoting treatment initiation by comparing rates of OTNY enrollment arriving through the caregiver campaign to rates of enrollment arriving through the patient campaign. Hypothesis: Engaging caregivers online will significantly increase the likelihood of promoting treatment initiation of individuals with FEP as compared to engaging prospective patients alone.

Throughout the campaign, one dedicated landing page for each unique target audience (prospective patients and caregivers), will be promoted online, presenting each audience with a unique and identifiable campaign phone line, email, text line, and live chat options. We will compare rates of inquiries, number of FEP referrals, and number of patients admitted to OTNY throughout NYS arriving through the caregiver campaign to rates of inquiries, number of FEP referrals, and number of patients admitted to OTNY arriving through the participant campaign. Both campaigns will run in parallel and

Version Date: 6.9.22 Page 14 of 31

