each will target a dedicated audience based on demographics (age) and online search query. For example, "I am hearing voices" will generate the participant ad/campaign, while "my daughter is acting strange" will generate an entirely different set of ads geared towards caregivers. Power Analysis: Current OTNY referral data suggest that caregivers including parents are 5 times more likely to initiate a referral inquiry as compared to prospective participants themselves. We therefore anticipate that at least 2/3 (66.7%) of campaign referrals (approximately 20 weekly) will be generated by the parent campaign. Based on OTNY referral data, we anticipate that 20% will be appropriate and all will be enrolled into OTNY. Sample size necessary to detect a prevalence of 66.7% for the caregiver campaign compared to the null hypothesis of equal rates for the two campaigns is 68, which has to be multiplied by the design effect (variance inflation factor), [1 + (n-1)p], to get required sample size. As ICC (p) ranges from 0.01 to 0.06, the design effect will range from 1.67 to 5.02 and the sample size required will vary from 114 to 342. Although there are 24 six-month time periods from all clusters (4 per cluster and 6 clusters, $4 \times 6 = 24$) based on the stepped wedge design for Aim 1, only 12 of them will have the campaign. Based on recent OTNY referral data, the number of enrolled subjects per cluster in a 6-month period varied from 26 to 34, with an average of approximately 30. Thus, we expect to have (30 x 12) 360 subjects enrolled from the campaign part of the stepped wedge design. This sample size will be sufficient to detect the hypothesized difference in rates (66.7% vs. 33.3%) at 80% power and α = 0.05, with an ICC as high as 0.06.

Aim 3: Explore which methods of online engagement are most effective at promoting treatment initiation by comparing rates of OTNY enrollment of individuals interacting with research staff via live chat or two-way video to rates of enrollment of individuals utilizing text, email, and/or phone alone. Hypothesis: individuals with FEP who engage via two-way video or live chat will be significantly more likely to initiate in-person contact compared to individuals with FEP who engage via text, email, and/or phone alone.

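### Aim 2 groups enrollees by the landing page or line they were served, which compares campaign yield; the hypothesis about engaging caregivers also needs the contact's role, which is not a listed field.

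*Combined protocol and SAP*

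**What the plan says.** Section 4 words the Aim 2 hypothesis by person: "Engaging caregivers online will significantly increase the likelihood of promoting treatment initiation for individuals with FEP as compared to engaging prospective patients online". Section 12 repeats it in nearly the same terms. The aim above it is worded by campaign: it compares enrollment arriving through the caregiver campaign with enrollment arriving through the patient campaign.

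The grouping variable is the campaign. Section 12 gives each of two landing pages its own channels, "presenting each audience with a unique and identifiable campaign phone line, email, text line, and live chat options". Section 11 says ads and pages are "displayed automatically based on the keywords/search terms entered by an individual user online as well as the age of individual searching", and Section 12 confirms that "each will target a dedicated audience based on demographics (age) and online search query". In its example, a query about a daughter's behavior "will generate an entirely different set of ads geared towards caregivers".

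Section 2 gives a wider audience than two pages suggest: "The campaign will target individuals as well as their friends, family, and caregivers, searching for information online".

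The Aim 2 power text starts from a figure about people, that "caregivers including parents are 5 times more likely to initiate a referral inquiry as compared to prospective participants themselves". It then infers that at least two thirds of campaign referrals will come through the parent campaign.

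The information staff record at contact is listed under Aim 3 in Section 12. It covers name and contact details, concerns, symptoms and their duration, the prospective patient's age, and the outcome. Relationship to the patient is not listed. The needs-assessment survey in Section 11 is optional.

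**The concern.** The page served and the role of the person making contact are different variables. They agree when the query reveals the role, as in the plan's two examples. They need not agree when a query names only a symptom, or when wording and age point different ways. The plan does not say how the two inputs combine. It also does not say on which side friends, siblings and partners are counted, and these people may fall in the 16 to 30 age range that Section 7 sets for patients.

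Some caregivers, friends or relatives can therefore be counted under the patient campaign, and some patients under the caregiver campaign. The step from the 5:1 inquiry ratio to the two-thirds campaign share relies on page tracking role, and no check of this is planned. At stake is whether an Aim 2 result can be read as a statement about engaging caregivers. Role not asked at contact may be hard to recover later.

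**Working it through.** **The plan's own figure.** Inputs from Section 12 (Aim 2): p1 = 66.7%, null 50%, α = 0.05, power 80%. For a two-sided one-sample z-test,

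n = [(1.96 × √0.25 + 0.842 × √(p1(1 − p1))) / (p1 − 0.5)]²

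With p1 = 0.667, n = [(0.980 + 0.397) / 0.167]² = 67.95, so 68. The plan's design effect 1 + (68 − 1) × ICC is 1.67 at ICC 0.01 and 5.02 at 0.06. Then 68 × 1.67 = 113.6 (114) and 68 × 5.02 = 341.4 (342). All stated figures reproduce.

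**Effect of misrouting on the share.** The documents give no misrouting rates, so these are assumptions. Let m be the fraction of caregiver-side contacts served the patient page, and s the fraction of patients served the caregiver page. With a true caregiver share of 2/3,

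observed caregiver-page share q = (2/3)(1 − m) + (1/3)s

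I take the plan's 360 subjects and its design effects as given. The effective sample sizes N are 360 / 5.02 = 71.7 and 360 / 1.67 = 215.6. Power in the hypothesized direction is Φ{[(q − 0.5)√N − 1.96 × 0.5] / √(q(1 − q))}.

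| m | s | q | Power, ICC 0.06 | Power, ICC 0.01 |
|---|---|---|---|---|
| 0 | 0 | 66.7% | 82% | 99.9% |
| 5% | 0 | 63.3% | 62% | 98% |
| 10% | 0 | 60.0% | 39% | 84% |
| 20% | 0 | 53.3% | 8% | 16% |
| 10% | 10% | 63.3% | 62% | 98% |
| 10% | 20% | 66.7% | 82% | 99.9% |
| 0 | 10% | 70.0% | 94% | above 99.9% |

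Worked case, m = 10%, s = 0, ICC 0.06: (0.1 × 8.468 − 0.980) / 0.490 = −0.272, and Φ(−0.272) = 0.39.

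**Reversal.** With s = 0, q falls below 50% when (2/3)(1 − m) < 1/2, that is m > 25%. If the 5:1 ratio is read as a true share of 5/6, then (5/6)(1 − m) < 1/2 needs m > 40%, and m = 20% still leaves (5/6)(0.8) = 66.7%.

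**If enrollment rates per contact are compared.** The aim's wording also allows this reading. Suppose the chance of enrolling depends on role only, and 2/3 of contacts are caregivers. The fraction of the true difference that remains is then the caregiver proportion on the caregiver page minus that on the patient page.

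- m = s = 10%: 0.600/0.633 − 0.067/0.367 = 0.947 − 0.182, so 77% remains.
- m = s = 20%: 0.533/0.600 − 0.133/0.400 = 0.889 − 0.333, so 56% remains.
- m = 10%, s = 20%: 0.600/0.667 − 0.067/0.333 = 0.90 − 0.20, so 70% remains, although the share itself is unchanged.

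**The case against.** The best defense is that the grouping matches the aim as stated. Aim 2 asks about the efficacy of a campaign directed at caregivers, and the page or line is the exposure delivered. Grouping by it is correct for that question, and regrouping the main test by a role learned only at contact would change the estimand. This stands, and it is why the campaign comparison should remain.

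A reader might infer that young friends, siblings and partners are counted as patients, so that the caregiver effect is diluted or reversed. The documents do not support this. Wording routes searchers as well as age, and the daughter example shows a query about someone else bringing up the caregiver ads. Nothing says that age prevails. Patients served the caregiver page would push the share the other way.

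The size also needs care. The 66.7% is a floor for the campaign share, not a measured share by role. The heavy losses of power belong to the highest ICC considered.

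Nor do the documents show that the error could never be detected. The contact list is introduced as an inclusion, not a complete set, and the 5:1 figure implies that OTNY referral data carry some record of role. But nothing ensures that role is recorded for every campaign contact, and no analysis uses it. Those two gaps remain.

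**Conclusion.** The point holds in a limited form. Aim 2 as planned compares the yield of two campaigns. It does not by itself support a conclusion about engaging caregivers versus prospective patients, because page is only a proxy for role and role is not a listed field. The contrast may be diluted, inflated or, in an extreme case, reversed.

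The figures are illustrations, since the rate and direction of misrouting are unknown. With one-way misrouting of 10% of caregivers and a true share of 66.7%, the observed share is 60.0%, with power of about 39% at ICC 0.06 and 84% at ICC 0.01. Reversal needs more than 25% one-way misrouting, or more than 40% if the true share is 5/6. Errors in the two directions can offset in the share, though not in a rate per contact.

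The plan's sample-size arithmetic is not at fault, and Section 12 names hypothesis A of Aim 1, not Aim 2, as the primary outcome. This is an inexpensive improvement, worth making because the missing information may not be recoverable later.

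**What to change.** Keep the comparison by campaign as the Aim 2 test of campaign yield.

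- Add one required field to the staff log at first contact, with two groups: prospective patient, or parent/guardian/other family/partner/friend. Count the second group as the caregiver side and record its sub-type.
- In Section 12, pre-specify a role-based version of the Aim 2 comparison as the analysis that supports any statement about engaging caregivers.
- Report a cross-table of page served by actual role, which shows the rate and direction of misrouting directly.

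The cost is one extra question in a log that staff already complete and a short addition to Section 12. Visitors who never contact staff will have no role recorded, so the role-based analysis covers contacts only.
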